4. STUDY SUMMARY

Study Title	A Pivotal, Randomized, Open-Label, 3-Period Crossover Study to Assess the Efficacy and Safety of AM-301 during House Dust Mite Challenge in an Environmental Exposure Chamber in Study participants with Perennial Allergic Rhinitis
Protocol Number	Sponsor Study Number: AM-301-CL-21-02 Ciantha Research Study Number: C2D01121
Study Phase	Pivotal Confirmatory Clinical Investigation
Study Objectives	Primary Objective To compare the efficacy of AM-301 Device between treated and non-treated subjects in the treatment of perennial allergic rhinitis (PAR) when evaluated in House Dust Mite (HDM) allergic study participants in an Environmental Exposure Chamber (EEC). Secondary Objective To compare the efficacy of AM-301 device between single and double applications per nostril of Altamira AM-301 Device in the treatment of perennial allergic rhinitis (PAR) when evaluated in House Dust Mite (HDM) allergic study participants in an Environmental Exposure Chamber (EEC).
Study Endpoints	Primary Efficacy Endpoint: Changes from baseline in TNSS at each post-dose assessment time points (0 to 3 hours) at Visit 3, Visit 4 and Visit 5 Secondary Efficacy Endpoints: 
• Difference of TNSS at individual timepoints during house dust mite challenge in the EEC (0-180 min) between single and double application of AM-301 and no treatment.• Change from baseline in individual NSS at Visit 3, Visit 4 and Visit 5• Patient reported Global rating for efficacy at single application and double application of AM-301 during EEC treatment visits.• Investigator reported Global rating for efficacy for single and double application of AM-301 during EEC treatment visits. Safety endpoints: 
• Occurrence and severity of Adverse Events (AEs) and Serious Adverse Events (SAEs).• Patient reported Global rating for tolerability at single application and double application of AM-301 during EEC treatment visits. Investigator reported Global rating for tolerability for single and double application of AM-301 during EEC treatment visits.
Study Design	Randomized, open label, 3-Period crossover trial. The clinical trial will consist of 5 visits, followed by a follow-up telephone call. The total period of the trial will be approximately 65 days. The 5 visits will be as follows: 
• Visit 1- Screening visit• Visit 2- EEC Screening Visit• Visit 3- Treatment Visit

	
 • Visit 4- Treatment Visit • Visit 5- Treatment Visit • Follow-up telephone call
Study Products and Study Sequence	
Study Product: AM-301 Nasal Spray
 
Treatment groups will be as follows:
 
A: One Spray of AM-301 per nostril
 
B: Two Sprays of AM-301 per nostril (with different spray angles)
 
C: No treatment
 
The study will consist of 6 study sequences:
 
 • Sequence 1 (n = 6): ABC • Sequence 2 (n = 6): BCA • Sequence 3 (n = 6): CAB • Sequence 4 (n = 6): ACB • Sequence 5 (n = 6): BAC • Sequence 6 (n = 6): CBA
Study population	Approximately 36 males and non-pregnant females, 18-65 years of age inclusive, with a History of Perennial Allergic Rhinitis (PAR) due to house dust mites.
Route of Administration	Intranasal
Confinement	Study participants will remain confined to the clinic for approximately 4-5 hours during each screening and treatment EEC visits.
Study Conduct	
The clinical trial will consist of 5 clinic visits; (1 medical screening, 1 EEC screening visit 3 EEC treatment visits).
 
Medical Screening Visit 1 (Day-28 to -1) At Visit 1, eligible study participants will first sign the informed consent document, complete all screening procedures, including inclusion and exclusion criteria and safety labs, and move on to Visit 2 if eligible for EEC screening.
 
EEC Screening Visit 2 (Day 1) At Visit 2, eligible study participants will have a nasal exam performed by the Investigator. Study participants will then enter the EEC for a total of 3 hours. Study participants will record their symptoms every 20 ± 5 minutes throughout the 3-hour EEC session.
 
Treatment Visit 3 (Day 8 + 2), Visit 4 (Day 15 + 2) and Visit 5 (Day 22+ 2) Eligible study participants will return for Visit 3 after at least 7 days after visit 2. Study Participants will be randomized at Visit 3. Subsequently study participants will return to the clinic for Visit 4 at least 7 days after Visit 3 and for Visit 5 at least 7 days after Visit 4. Treatment will occur on site performed by trained clinical staff. Study participants will enter the EEC on these visits following administration, but no later than 10 minutes after

	
treatment administration and will record their symptoms every 20 minutes throughout the 3-hour EEC session.
 
Following the assessments at Visit 5, this will conclude the study. AE's will also be recorded throughout each visit .
 
Follow-Up Telephone Call
 
Follow-up Telephone call will be done after approximately 7 + 2 days of completion of Visit 5.
 
The following assessment will be conducted:
 
 • Subjects will be asked for any occurrence of adverse events after last treatment administration. • Subjects will be asked if they have taken any concomitant medications since last treatment administration.
Inclusion Criteria	
 1. Study participants must be willing and able to give their signed and dated written informed consent to participate in the study prior to commencing any study-related activities 2. Male and female study participants aged 18-65 years at the time of Informed consent and medical screening will be included in the study. Women will be considered for inclusion if they are 
 • Not pregnant, as confirmed by pregnancy test at visit 1, not nursing and not planning to become pregnant over the duration of the study. • Of non-child bearing potential (i.e. physiologically incapable of becoming pregnant, including any female who is post-menopausal, surgically sterile with documented proof of hysterectomy or tubal ligation or bilateral oophorectomy or meets clinical criteria for menopause and has been amenorrhoeic for more than 1 year prior to the screening visit). • WOCBP must use effective methods of birth control starting at least 1 month prior to the Screening Visit 1 and until 72 hours after the last study procedure, such as total abstinence, hormonal or non-hormonal intrauterine device, a double-barrier method (Condom and diaphragm/cervical with spermicide (foam, cream, gel, sponge)), oral, transdermal, injected or implanted hormonal contraceptive. A sterile sexual partner is not considered an adequate form of birth control. 3. Body mass index between 18.0 and 32.0 kg/m² inclusive. 4. History of perennial allergic rhinitis to house dust mite for more than 1 year. 5. Positive Skin Prick Test (SPT) for Dermatophagoides pteronyssinus (der p) allergen at screening or within 12 months prior to the screening visit. Test will not be repeated if they have been performed at Cliantha Research in previous 12 months. 6. Spirometry will be performed at Screening. Study participants must have an acceptable spirometry assessment showing FEV1 that is ≥80% of the predicted GLI-2012 value and a Tiffeneau ratio (FEV1/FVC ratio [FEV1%]) of ≥0.7 performed as per American Thoracic Society (ATS) standards to be eligible for the study. 7. Adequate level of rhinitis symptoms in a house dust mite challenge, defined as a change in TNSS of at least 4 units over pre-EEC TNSS on at least two time points within the 3-hour screening house dust mite challenge (Visit 2).

	
 8. Total Nasal Symptom Score (TNSS) of ≤ 4 prior to entering the house dust mite chamber at screening EEC Visit 2. 9. Smokers need to be able to refrain from smoking six hours before the allergen challenge during all EEC visits 10. Agree to abide by the study restrictions and return for the required assessments and must be willing to comply with study procedures and study protocol.
Exclusion Criteria	
 1. Any clinically relevant abnormal findings in physical examination, clinical chemistry, hematology, urinalysis, vital signs, lung function at screening visit, which, in the opinion of the investigator, may either put the subject at risk because of participation in the study or may influence the results of the study, or the subject's ability to participate in the study. 2. Use of any medication considered to have an influence on the outcome of the study during the EEC session, at the discretion of the Investigator and/or designee. 3. Recent nasal ulcers, mucosal erosion, nasal surgery, or nasal trauma, that might interfere with study results as determined by the Investigator and/or designee. 4. Past or present concomitant medical conditions, which as judged by the investigator, may affect the outcome of this study. These diseases include, but are not limited to, cardiovascular disease, malignancy, hepatic disease, renal disease, hematological disease, neurological disease, endocrine disease or pulmonary disease (including but not confined to chronic bronchitis, emphysema, tuberculosis, bronchiectasis or cystic fibrosis). 5. Allergen-specific Immunotherapy (SIT) within 2 years prior to the study. 6. Any upper respiratory tract infection (including rhinitis and sinusitis) in the last 14 days before entering the study Visit 1. 7. Asthmatics will be excluded from the study. 8. Conditions or factors, which would make the subject unlikely to be able to stay in the EEC for 3 hours. 9. Any medical condition or concomitant medication that makes the use of adrenaline less effective (e.g. use of local and systemic beta-blockers, ACE inhibitors). 10. Known sensitivity to the constituents of AM-301 like Propylene glycol or Mannitol. 11. Treatment with antipsychotic medications with antihistaminic effect (e.g. chlorpromazine, levomepromazine, clozapine, olanzapine, tiordiazine). 12. Participation in another clinical trial 30 days prior to enrollment. 13. History of drug or alcohol abuse within the last two years. 14. Risk of non-compliance with study procedures. 15. Suspected inability to understand the protocol requirements, instructions and study-related restrictions, the nature, scope, and possible consequences of the study. 16. History of an acute infection four weeks prior to Visit 1. 17. Study participants with severe septum deviation or other structural nasal abnormalities that prevent the intranasal administration of a medical device.

	
18. Subject has a positive result for SARS-CoV-2 and/ or has clinical signs and symptoms consistent with COVID-19 infection, e.g., fever, dry cough, dyspnea, sore throat, fatigue, muscle or body aches and gastrointestinal symptoms or confirmed infection by appropriate SARS-CoV-2PCR test within the 2 weeks prior to visit 1.
 
19. Study participants who have taken COVID-19 Vaccine 3 days or less prior to a visit.
 
20. Study participants that have a relationship dependency with the Sponsor or study site staff.

Statistical Analysis	
For applicable endpoints, the treatment comparison between treated and non-treated will be performed using a mixed-effects Analysis of Covariance Model (ANCOVA) for a crossover study for 3 periods. The model will include Treatment, Period (Visit) and Sequence as fixed effects, baseline (pre-dose) measurement as a covariate. Subject nested within treatment sequence will be fitted as a random effect. LS means and SEs by treatment arm will be extracted from the model and presented. Further, contrasts between LS means will be extracted for (i) (1-spray+2-sprays)/2 vs no treatment (ii) 1-spray vs no treatment and (iii) 2-sprays vs no treatment. The 95% CI and 2-sided p-values will be provided for each of these contrasts.
 
Appropriate statistical analysis will be performed to analyze the global rating scales for efficacy and tolerability.
 
Safety Population: All study participants who are randomized will be included in the Safety population.
 
Intent to Treat (ITT) Population: All study participants in the Safety Population who provide at least one TNSS assessment will be included in ITT population.
 
Per Protocol (PP) Population: PP Population will include all study participants in ITT who completed the study and do not have any major protocol violations.
 
The analyses of all efficacy endpoints will be carried out using the ITT population. Supportive analyses will also be provided for the primary endpoint using the PP population.

Safety Analysis	Safety analysis will include descriptive analysis and listings according to received treatment.
Sample Size Determination	It is hypothesized that the Total Nasal Symptom Score (TNSS) over 180 min post treatment with no treatment is 2.3 units as compared to 1.0 and 1.6 units for, respectively, 2-sprays and 1-spray of AM-301. Assuming the SD of the within subject change is 2 units, N=30 randomized subjects will provide 87.4% power at the 2-sided 5% alpha level to test the hypothesis that the TNSS score averaged across 1-spray and 2-sprays is superior to no treatment. Sufficient numbers of volunteers will be screened to randomize approximately 36 study participants to have 30 completed study participants.

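### The only secondary objective, one spray against two sprays, has no planned contrast: intervals and p-values are specified only against no treatment

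*Combined protocol and SAP*

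**What the plan says.** All references are to section 4, Study Summary.

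- **Study Objectives.** The single secondary objective is "To compare the efficacy of AM-301 device between single and double applications per nostril of Altamira AM-301 Device".
- **Statistical Analysis, model.** For applicable endpoints, "the treatment comparison between treated and non-treated will be performed using a mixed-effects Analysis of Covariance Model". Treatment is a fixed effect with all three arms, and LS means with SEs are presented by arm.
- **Statistical Analysis, contrasts.** The list is "i) (1-spray+2-sprays)/2 vs no treatment (ii) 1-spray vs no treatment and (iii) 2-sprays vs no treatment". The inference attaches to that list: "The 95% CI and 2-sided p-values will be provided for each of these contrasts".
- **Secondary Efficacy Endpoints.** The first is a TNSS difference at individual timepoints "between single and double application of AM-301 and no treatment".
- **Global ratings.** The only analysis text is "Appropriate statistical analysis will be performed to analyze the global rating scales for efficacy and tolerability".
- **Sample Size Determination.** The assumed TNSS is 2.3 with no treatment, against "1.0 and 1.6 units for, respectively, 2-sprays and 1-spray of AM-301". Power is claimed only for the mean of the two regimens against no treatment.

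**The concern.** The objective asks whether two sprays differ from one. Every contrast that receives an interval and a p-value asks whether something differs from nothing. Two other texts come near the objective without settling it. The first secondary endpoint can be read as each regimen against no treatment or as all three pairs, and it defines a variable rather than an analysis. The global efficacy ratings have no named comparison.

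Followed as written, the report would show each regimen against no treatment and leave the secondary comparison to the reader. The tempting shortcut is to conclude that two sprays work better because two are significant and one is not. That is not a test of the difference between them, and nothing in the planned output guards against it.

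**Working it through.** **Inputs (Sample Size Determination).** Means 2.3 (none), 1.6 (1-spray), 1.0 (2-sprays); SD of the within-subject change 2; 30 completers, about 36 randomized; two-sided 5%.

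**1. Reproduce the stated power.** Read SD 2 as the SD of the difference between two periods, so the within-subject error variance is 2²/2 = 2.

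- Difference for the mean of the two regimens against none: 2.3 − (1.6 + 1.0)/2 = 1.0.
- SE = √(1.5 × 2/30) = 0.316; noncentrality 1.0/0.316 = 3.16.
- Error df = 90 − 1 − 29 − 2 − 2 = 56 (observations less mean, subjects, periods, treatments).
- Noncentral t power: 87.4%, as stated. Reading SD 2 as the per-period residual SD gives 59.4%, and as the SD of the averaged contrast itself 76.8%; neither matches.

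**2. Can the missing contrast be recovered?** Write (ii) and (iii) for the two single-regimen contrasts; (i) is their mean. The estimate is (iii) − (ii). Because 4Var(i) = Var(ii) + Var(iii) + 2Cov,

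Var[(iii) − (ii)] = 2Var(ii) + 2Var(iii) − 4Var(i).

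Check: 2(4/30) + 2(4/30) − 4(3/30) = 4/30, so SE = 0.365. It is recoverable, but only by combining three contrast variances. The per-arm SEs alone do not give it in a crossover.

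**3. Precision of a direct contrast, planned difference 1.6 − 1.0 = 0.6.**

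| Completers | df | SE | 95% CI half-width | Power |
|---|---|---|---|---|
| 30 | 56 | 0.365 | 0.73 | 36.5% |
| 36 | 68 | 0.333 | 0.67 | 42.7% |

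About 88 to 90 completers would be needed for 80% power.

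**4. How often the shortcut misleads.** Simulation of the three contrasts with a shared variance estimate; df 56 at n = 30; 1,000,000 replicates for the two scenarios at n = 30 with common benefit 1.0 and with the planned means, 400,000 for common benefit 0.7 and 1.3.

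| Truth | n | Exactly one regimen significant against none |
|---|---|---|
| Equal, both 0.7 better than none | 30 | 33% |
| Equal, both 1.0 better | 30 | 24% |
| Equal, both 1.3 better | 30 | 9% |
| Equal, both 1.0 better | 36 | 19% |

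With equal regimens, both 1.0 better and n = 30, the direct contrast is significant in 5% of all trials and in 13% of the discordant ones.

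At the planned means, 2-sprays is significant and 1-spray is not in 47% of trials. In 45% of those the direct contrast is not significant.

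**The case against.** The strongest points on the other side are these.

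- **Only the Study Summary was available for review.** A fuller statistical section might list the contrast. This limits the finding to that text. But the summary already gives the model, covariate, random effect and an enumerated contrast list, so the omission sits inside a detailed specification.
- **The contrast list may have been meant for the primary objective only.** Its opening echoes that objective. If so, the secondary objective has no analysis text at all, which does not help the plan.
- **The comparison is partly covered.** The model includes all three arms, the endpoint wording can be read as all pairs, and the difference is derivable. All true. What is missing is a direct result that is pre-specified, reported and tied to the objective.
- **The simulations describe a reader's error.** The plan does not commit to that error, and the equal-regimen scenarios depart from its assumed means. They show how easily the planned outputs invite a wrong reading; they do not show bias in any planned estimate.
- **The figures use the planning values for TNSS over 180 minutes.** The endpoint that mentions both regimens is at individual timepoints, for which no difference or SD is given. The figures should therefore not be carried over to single timepoints.
- **Low power for a secondary comparison is not an error.** Agreed: the plan claims power only for the pooled contrast, and that figure reproduces.

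**Conclusion.** The concern holds for the text reviewed and should be fixed. The omission is established by the wording alone and does not depend on the power calculations. The numerical size rests on reading SD 2 as a paired-difference SD, which the reproduced power supports. Under the weaker reading as a per-period residual SD, direct power for the planned difference would fall to about 21% at 30 completers and 24% at 36. On either reading the trial can estimate the difference between regimens but is not sized to establish it. The gap concerns the secondary objective and how its results will be read.

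**What to change.** 1. Add contrast (iv), 2-sprays minus 1-spray, from the same mixed model and for the same endpoints as (i) to (iii), with a 95% CI and two-sided p-value. Name it as the analysis of the secondary objective.
2. Reword the first secondary endpoint so that it lists the pairwise comparisons meant.
3. State that contrast (iv) is mainly for estimation and give its expected precision: at 30 completers, half-width about 0.73 and power about 37% for the planned 0.6. If a formal claim is wanted from it, say where it stands in the testing order.
4. State that significance of one regimen but not the other against no treatment will not be read as a difference between them.

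The cost is one more contrast from a model already fitted and a few sentences, before database lock. The downside is that the stated power is unflattering, and the CI half-width exceeds the planned difference even if all 36 participants complete.

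### The primary endpoint is the TNSS change at each of about nine time points, but the trial is powered for one 0-180 minute value and one pooled contrast

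*Combined protocol and SAP*

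**What the plan says.** All references are to section 4, Study Summary, which is the text supplied.

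- **Study Endpoints, primary:** "Changes from baseline in TNSS at each post-dose assessment time points (0 to 3 hours) at Visit 3, Visit 4 and Visit 5". No mean, area under the curve or peak is named.
- **Study Endpoints, first secondary:** "Difference of TNSS at individual timepoints during house dust mite challenge in the EEC (0-180 min) between single and double application of AM-301", with the untreated condition as a further comparator. Time-point TNSS therefore appears at both levels.
- **Study Conduct:** at treatment visits participants "will record their symptoms every 20 minutes throughout the 3-hour EEC session".
- **Study Objectives, primary:** "To compare the efficacy of AM-301 Device between treated and non-treated subjects".
- **Sample Size Determination:** "It is hypothesized that the Total Nasal Symptom Score (TNSS) over 180 min post treatment with no treatment is 2.3 units", against 1.0 for two sprays and 1.6 for one spray. With an SD of 2 units, 30 participants are said to give 87.4% power at two-sided 5% "to test the hypothesis that the TNSS score averaged across 1-spray and 2-sprays is superior to no treatment".
- **Statistical Analysis:** a mixed-effects ANCOVA with treatment, period, sequence and pre-dose baseline, and a random participant effect. Then "contrasts between LS means will be extracted for (i) (1-spray+2-sprays)/2 vs no treatment", followed by each spray arm against no treatment, each with a confidence interval and p-value. The model has no time term and its outcome variable is not named.

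**The concern.** The stated primary endpoint is not the quantity that was powered. Read literally, it produces about nine primary tests, and the text does not say whether one, all or a summary of them must succeed. The choice decides what the trial's error rates are. If any one may succeed without adjustment, the 5% level in the sample-size statement is lost. If the tests are adjusted, or all must succeed, the 87.4% power no longer applies. The analysis model does not settle this, because it can be fitted to one visit-level summary or separately at each time point.

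The ambiguity matters more here than in many trials. This is an open-label pivotal study against no treatment, with symptoms scored by the participants themselves, so room to choose the time point or summary after seeing the data would weaken the result.

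**Working it through.** **Inputs from the documents.** TNSS 2.3 (no treatment), 1.6 (one spray), 1.0 (two sprays); SD of the within-participant change 2; N = 30; two-sided alpha 0.05; readings every 20 minutes over 180 minutes, so 180/20 = 9.

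**Assumptions.** The documents give no correlation between readings, so exchangeable values of 0.1, 0.5 and 0.9 are used. SD 2 is read as the SD of a within-participant difference between two treatments, because that reading reproduces the stated power.

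**Step 1: the stated power.**
- Difference: 2.3 − (1.0 + 1.6)/2 = 1.0.
- Residual variance per period: 2²/2 = 2.
- Variance factor of the pooled contrast: 1/4 + 1/4 + 1 = 1.5.
- SE = √(1.5 × 2/30) = 0.316.
- Degrees of freedom: 89 − 29 (participants) − 2 (periods) − 2 (treatments) = 56.
- Noncentral t power: 87.44%, against 87.4% stated.

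The figure is correct for one test of one value. The arithmetic would be the same for any single value with effect 1.0 and SD 2; it is the sample-size wording that points to a visit-level value.

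**Step 2: false positives over nine readings.** With independent tests, 1 − 0.95⁹ = 37.0%. Simulating the balanced six-sequence, three-period design under no effect (N = 30, 40,000 trials per setting) gives:

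| Assumed correlation | 0.1 | 0.5 | 0.9 |
|---|---|---|---|
| Any of nine, unadjusted, two-sided | 36.9% | 27.3% | 12.6% |
| Any of nine, in favour of AM-301 | 19.5% | 13.7% | 6.2% |
| Any of nine, Bonferroni | 4.7% | 4.0% | 1.8% |
| One visit mean | 4.9% | 5.1% | 5.0% |

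N = 36 gives 36.4%, 27.1% and 12.9% for the first row. A serial AR(1) correlation of 0.5, 0.8 or 0.95 gives 32.7%, 23.7% and 13.5%.

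**Step 3: power.** Bonferroni alpha is 0.05/9 = 0.0056. The documents do not say whether SD 2 belongs to a single reading or to the 0-180 minute mean, so both are shown. An effect of 1.0 at every reading is assumed, with N = 30. If SD 2 belongs to the mean, the single-reading SD is 2 × √(9/(1 + 8ρ)), where ρ is the correlation.

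| Assumed correlation | 0.1 | 0.5 | 0.9 |
|---|---|---|---|
| **SD 2 at each reading** | | | |
| One given time point, unadjusted | 87.4% | 87.4% | 87.4% |
| One given time point, Bonferroni | 61.1% | 61.1% | 61.1% |
| All nine required | 35.1% | 54.5% | 75.6% |
| Visit mean | 100% | 98.7% | 89.9% |
| **SD 2 for the visit mean** | | | |
| Implied single-reading SD | 4.47 | 2.68 | 2.10 |
| One given time point, unadjusted | 28.5% | 63.9% | 84.3% |
| One given time point, Bonferroni | 8.0% | 31.0% | 55.6% |
| All nine required | <0.1% | 19.7% | 70.6% |
| Visit mean | 87.5% | 87.5% | 87.5% |

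With SD 2 at each reading, Bonferroni power at N = 36 is 72.3%, and 49 completers would be needed to restore 87.4% at a given time point.

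**The case against.** The strongest reply is that a time average was plainly meant. The model has no time term and reports one least-squares mean per arm. The sample-size statement gives one value per arm. Individual time points are listed separately as secondary, which would be redundant if they were also primary. The values 2.3, 1.6 and 1.0 are in TNSS units, and inclusion criterion 7 asks for a rise of at least 4 units at two screening readings, so a raw sum or area is unlikely. On this view the fault is loose endpoint wording.

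That is a fair account of the probable intent, and it is why the fix is easy. But no sentence states it, and a confirmatory primary variable should not have to be inferred against its own definition.

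Other points stand in part:
- The pooled contrast can be identified from the primary objective and the sample-size statement, and it is listed first of the three. Only an explicit primary label is missing.
- No passage proposes that any one reading suffices or that all nine are required. These are consequences of leaving the rule open.
- A correlation of 0.1 between readings 20 minutes apart is low, so 13% to 27% is the more plausible part of the range. Even 13% is more than twice the nominal 5%.
- A constant 1.0-unit effect from the first reading is an assumption.
- Only the study summary was supplied, so a fuller rule elsewhere cannot be excluded. The primary endpoint and the sample-size statement nevertheless disagree within that summary.

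**Conclusion.** The concern holds: the primary endpoint is wrong as written. The 5% level and 87.4% power belong to one 0-180 minute value tested with one pooled contrast, not to TNSS at each time point. The power calculation itself is correct. Taken literally, the endpoint gives a 13% to 37% chance of at least one false positive if any reading may succeed unadjusted (6% to 19% in favour of AM-301). With SD 2 at each reading, power is 61% at a given time point after Bonferroni, or 35% to 76% if all nine must succeed. It is lower if SD 2 belongs to the visit mean. These ranges rest on nine readings, N = 30, assumed exchangeable correlations of 0.1 to 0.9 and, for power, a constant 1.0-unit effect. The mismatch between endpoint and sample size depends on none of these.

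**What to change.** 1. In Study Endpoints, define the primary variable as one value per participant per treatment visit, for example the mean change from pre-dose TNSS over 0-180 minutes, with a rule for missing readings.
2. Have the sponsor confirm that this is the quantity behind 2.3, 1.6, 1.0 and the SD of 2, since the sample-size statement does not say mean or area, score or change. Score or change does not alter the test, because the pre-dose value is already a covariate. A mean and a trapezoid area from the same readings are nearly interchangeable (correlation at least 0.987 in simulation).
3. In Statistical Analysis, name this variable as the outcome and label contrast (i) as the single primary test.
4. Keep individual time points as secondary only. If they are modelled jointly, add time, treatment-by-time and a within-visit covariance.

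If the sponsor wants time points to remain primary, the success rule and adjustment must be stated and the sample size recalculated.

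The recommended change costs wording and programming. Visits, readings and sample size stay the same, and the stated alpha and power then apply, subject to step 2. The downside is that time-point results become secondary.

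### Do open-label investigator ratings compromise the comparison of one spray with two?

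*Combined protocol and SAP*

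**What the plan says.** All of this stands in section 4, Study Summary, the only part of the plan available here.

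- **Study Design:** "Randomized, open label, 3-Period crossover trial". The study title also says open label.
- **Secondary efficacy endpoint:** "Investigator reported Global rating for efficacy for single and double application of AM-301 during EEC treatment visits".
- **Safety endpoint:** "Investigator reported Global rating for tolerability for single and double application of AM-301 during EEC treatment visits".
- **Secondary objective:** "To compare the efficacy of AM-301 device between single and double applications per nostril of Altamira AM-301 Device".
- **Study Conduct, treatment visits:** "Treatment will occur on site performed by trained clinical staff". The text does not say whether the rating investigator is present at dosing or is told the spray count.
- **Statistical Analysis, TNSS model:** the listed contrasts are "i) (1-spray+2-sprays)/2 vs no treatment (ii) 1-spray vs no treatment and (iii) 2-sprays vs no treatment", so each one is against no treatment.
- **Statistical Analysis, ratings:** "Appropriate statistical analysis will be performed to analyze the global rating scales for efficacy and tolerability". This one sentence covers patient and investigator ratings together.
- **Sample Size Determination:** the assumed TNSS values are "no treatment is 2.3 units as compared to 1.0 and 1.6 units for, respectively, 2-sprays and 1-spray of AM-301".

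**The concern.** Both investigator ratings are listed for the two spray conditions only, so one spray against two is the natural comparison for them, and for efficacy that comparison is also the secondary objective. The sample size section assumes a better TNSS with two sprays, so the plan itself carries an expectation in that direction. A rater who knows the spray count and shares that expectation could score two sprays higher with no true difference.

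The sentence on the analysis of the ratings does not rule out a significance test between spray counts. TNSS has little power for that comparison, so a significant investigator rating might be taken as the answer to the secondary objective although it could not separate effect from expectation. At stake would be a claim that two sprays work better than one.

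**Working it through.** **1. Reproduce the plan's power.** Inputs from Sample Size Determination: TNSS 2.3 (no treatment), 1.6 (one spray), 1.0 (two sprays), SD of the within-subject change 2, N = 30, two-sided 5%.

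- Difference for the pooled contrast: 2.3 − (1.0 + 1.6)/2 = 1.0.
- Reading the SD of 2 as that of a difference between two periods, the per-period variance is 2²/2 = 2.
- Contrast variance: 2 × (1/4 + 1/4 + 1)/30 = 0.10, so SE = 0.316 and the noncentrality is 1.0/0.316 = 3.162.
- Residual df: 90 − 1 − 29 − 2 − 2 = 56.
- Power from the noncentral t: 87.4%, as stated. Reading the SD of 2 as per period gives about 59%, so the paired-difference reading is the one that fits.

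**2. TNSS power for one spray against two, same reading.** Difference 1.6 − 1.0 = 0.6.

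| N | SE | df | Power |
|---|---|---|---|
| 30 | 2/√30 = 0.365 | 56 | 36.5% |
| 36 | 2/√36 = 0.333 | 68 | 42.7% |

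This shows that TNSS is weak for the secondary objective. It says nothing about how the investigator rating behaves.

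**3. What a rater shift would do, if there were one.** Assume no true difference and a shift of b SDs of the paired rating difference. Use a two-sided 5% paired t test with noncentrality b√n and n − 1 df.

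| b (assumed) | Rejection, n = 30 | Rejection, n = 36 |
|---|---|---|
| 0 | 5.0% | 5.0% |
| 0.1 | 8.3% | 9.0% |
| 0.2 | 18.5% | 21.5% |
| 0.3 | 35.6% | 41.7% |

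An observed mean shift of 2.045/√30 = 0.373 SD (30 pairs) or 2.030/√36 = 0.338 SD (36 pairs) gives p = 0.05. These two values are only the critical value divided by √n. They hold for any paired test of that size and do not measure rater bias. The values of b have no anchor in the documents, and the rating scale is not given, so the t test is itself an assumption.

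**4. Set the passages against the claim.** For the harm to occur, four things must happen: a test of the investigator rating between spray counts is run, TNSS is inconclusive, the rating is significant, and it is then given too much weight. Step 2 makes the second plausible. The first is not planned: no one-versus-two contrast is listed for any endpoint, and no test is named for the ratings. The third and fourth depend on the first.

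**5. Look at the expectation itself.** The values 1.0 and 1.6 are sample size assumptions for TNSS and do not show what site raters believe. They say nothing about tolerability, where more spray might equally be expected to look worse. Tolerability is also a safety endpoint and lies outside the secondary objective, which concerns efficacy.

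**The case for a change.** The best case for the concern is that declaring a trial open label does not settle what a rater-dependent endpoint may be used to show. In a study labelled pivotal and confirmatory, the role of these ratings should be fixed before data are seen. A short rule would do it: tabulate the investigator ratings by spray count without a p-value, mark them as open label, and record whether the rater knew the spray count.

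Part of this stands. Within the summary the analysis of the global ratings is unspecified, and a fuller analysis section would normally name the method. That is a general remark on pre-specification. It applies to patient and investigator ratings alike, and a synopsis is not where such detail is usually found.

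The rest does not carry. Leaving out a p-value removes no bias, because the tabulated within-participant differences contain the same shift. An open-label mark repeats the design row, and a field on rater awareness has no stated use in the analysis. Participants receive the sprays and record their own symptoms, so expectation can act on the patient rating too. Barring a test for one rating and leaving the other under the same sentence is a preference on which statisticians may differ. Masking the rater is the only step that could reduce bias. It depends on site roles the summary does not describe, and it would help only in part, by an unknown amount, because the participants know what they received.

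**Conclusion.** The concern does not hold. Unmasked investigator ratings follow from a design choice that the plan states openly. Nothing in the text contradicts that choice, and no test of those ratings between spray counts is planned.

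The arithmetic is sound but does not size a defect. The 36.5% (N = 30) and 42.7% (N = 36) describe TNSS power for one spray against two, which is a different question. The inflated rejection rates rest on assumed shifts, an unstated rating scale and a test the plan does not name. The actual rater bias cannot be computed from the documents.

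What is left is missing detail on one secondary efficacy rating and one safety rating. The primary TNSS contrast is not affected, and its 87.4% power reproduces. This conclusion rests on the Study Summary alone. Had the documents relied on a significance test of the investigator rating to support two sprays over one, the judgement would be different.
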